### **5.2.1.** Analyses for Continuous Endpoints

Continuous variables will be presented using summary statistics: number of observations, arithmetic mean, standard deviation, cv%, median, minimum and maximum values.

Log transformed continuous variables will be presented using summary statistics: number of observations, arithmetic mean, median, cv%, standard deviation, minimum, maximum, geometric mean and geometric cv%.

### 5.2.2. Analyses for Categorical Endpoints

Categorical variables will be presented using summary statistics: number of observations, counts and percentages.

### 5.2.3. Mixed Model for Repeated Measurements (MMRM)

An MMRM model will be used with treatment, time (as a factor), treatment-by-time interaction, baseline and baseline-by-time interaction as fixed effects. Time will be fitted as a repeated effect within each participant\*period. Baseline will be included as two separate variables, the average baseline for the participant, and the deviation of each treatment period baseline from the average baseline for each participant. An unstructured covariance matrix will be fitted to the repeated times within participant (other covariance matrices will be considered if necessary, e.g. if the model does not converge).

The Least Squares (LS) means (and standard errors, 90% confidence intervals and 2-sided p-values) will be obtained for each treatment at each timepoint. Differences (and standard errors, 90% confidence intervals and 2-sided p-values) between LS means will also be obtained, comparing each dose versus placebo. If data have been logged, LS means and differences (including CI's) will be back transformed to give percent changes from baseline ([relative change from baseline -1]\*100), and percent change from placebo ([ratio of relative change from baseline -1]\*100).

Example SAS code is provided in Appendix 2.

#### Statistical Model Diagnostics

The presence of outliers will be investigated for this model. An outlier will be defined as any response data value with a studentized (conditional) residual greater than 3, or less than -3. A listing will be presented of any participants meeting these criteria and will be included with standard SAS output. The assumptions of normality will be verified graphically using residual plots. For each fitted model, a set of conditional studentized residual plots will be produced, including residual plot, histogram of normality, quartile-quartile (QQ) plot and summary of fit statistics. The residual plots will not be included in the CSR.

If there are outliers or major deviations from normality, then the effect of these on the conclusions may be investigated through alternative transformations and/or analyses excluding outliers. Justification for any alternative to the planned analysis will be given in the report of the study.

### 5.2.4. Mixed Effects Analysis of Variance (ANOVA)

A mixed effects ANOVA with treatment as a fixed effect and participant as a random effect will be used for the analysis of PK endpoints.

Least square (LS) estimates of the group means and mean differences along with standard errors, 90% confidence intervals and p-values will be presented, which will be backtransformed for data that was natural log-transformed prior to analysis.

A figure showing the (back-transformed) LS means (with 90% confidence intervals) vs group will be produced.

Example SAS code is provided in Appendix 2.

Statistical model diagnostics as described in Section 5.2.3 would also be conducted for these analyses.

#### 5.2.5. Mixed Effects ANCOVA

A mixed effects model with treatment as a fixed effect, baseline as a covariate and participant as a random effect will be used. Estimates of the adjusted mean differences (Test-Reference) and corresponding 90% confidence intervals will be obtained from the model. The adjusted mean differences and 90% confidence intervals for the differences will be exponentiated to provide estimates of the ratio of adjusted geometric means (Test/Reference) and 90% confidence intervals for the ratios.

Example SAS code is provided in Appendix 2.

Statistical model diagnostics as described in Section 5.2.3 would also be conducted for these analyses.

### 5.3. Methods to Manage Missing Data

### 5.3.1. Missing Safety Data

For the analysis of safety endpoints, the sponsor data standard rules for imputation will be applied.

### 5.3.2. Missing Pharmacokinetic (PK) Data

In all PK data presentations (except listings), concentrations below the limit of quantification (BLQ) will be set to zero. In listings, BLQ values will be reported as "<LLQ", where LLQ will be replaced with the value for the lower limit of quantification (LLQ).

For PK summary tables and plots of mean/median profiles, statistics will be calculated having set concentrations to missing if 1 of the following cases is true:

- 1. A concentration has been collected as ND (ie not done) or NS (ie no sample),
- 2. A deviation in sampling time is of sufficient concern or a concentration has been flagged anomalous by the pharmacokineticist/statistician.

Note that summary statistics will not be presented at a particular timepoint if more than 50% of the data are missing.

If a PK parameter cannot be derived from a participant's concentration data, the parameter will be coded as NC (ie not calculated). (Note that NC values will not be generated beyond the day that a participant discontinues). In summary tables, statistics will be calculated by setting NC values to missing; and statistics will be presented for a particular dose with ≥3 evaluable measurements. For statistical analyses (i.e. mixed effects model), PK parameters coded as NC will also be set to missing; and analyses will not be performed for a particular parameter if more than 50% of the data are NC.

If an individual participant has a known biased estimate of a PK parameter (due for example to an unexpected event such as vomiting before all the compound is adequately absorbed in the body), this will be footnoted in summary tables and will not be included in the calculation of summary statistics or statistical analyses.

#### 6. ANALYSES AND SUMMARIES

#### 6.1. Primary Endpoint(s)

The primary endpoints are related to safety/tolerability and their analyses are described in Section 6.6.

#### 6.2. Secondary Endpoint(s)

The secondary endpoints as listed in Section 2.2 are related to PK and their analyses are described in Section 6.3.1.

#### **6.3. Other Endpoints**

#### 6.3.1. PK Endpoints

 $t_{1/2}$ 

The PK parameters detailed in Section 3.3.1 will be listed and summarized for participants in the PK Parameter Analysis Set (as defined in Section 4). Missing values will be handled as detailed in Section 5.3. Each PK parameter will be summarized by dose (and fasting condition, if appropriate) as applicable. Each summary will include the set of summary statistics as specified in Table 4.

Parameter	Summary Statistics
AUC last , AUC inf , C max , CL/F,	N, arithmetic mean, median, cv%, standard deviation,
$V_z/F$ , $AUC_{last}(dn)$ ,	minimum, maximum, geometric mean and geometric
$AUC_{inf}(dn), C_{max}(dn)$	cv%.
T	N median minimum mayimum

arithmetic mean, median,

standard

deviation.

Table 4. PK Parameters to be Summarized Descriptively

The plasma PK parameters will be summarized descriptively by dose (and fasting condition, if appropriate) as applicable. Dose-normalized AUCinf, AUClast, and Cmax will be plotted against dose (and fasting condition, if appropriate) using a logarithmic scale, and will include individual participant values and the geometric means for each dose. These plots will be used to understand the relationship between the PK parameters and dose (and fasting condition, if appropriate).

minimum, maximum.

Geometric means will have a different symbol than the individual values. A footnote will be added to the plots to indicate that geometric means are presented. All dose normalized parameters will be listed along with other individual PK parameters.

Supporting data from the estimation of  $t_{1/2}$  will be listed by treatment and dose where applicable: terminal phase rate constant ( $k_{el}$ ); goodness of fit statistic from the log-linear regression ( $r^2$ ); the percent of AUCinf based on extrapolation (AUCextrap%); and the first, last, and number of time points used in the estimation of  $k_{el}$ . These data may be included in the CSR.

Presentations for PF-07328948 concentrations will be presented using participants in the PK Concentration Set (as defined in Section 4) and will include:

- a listing of all concentrations sorted by participant ID, dose and nominal time post-dose. The concentration listing will also include the actual times. Deviations from the nominal time will be given in a separate listing.
- a summary of concentrations by dose and nominal time post-dose, where the set of statistics will include n, mean, median, standard deviation, coefficient of variation (cv), minimum, maximum and the number of concentrations above the lower limit of quantification.

- individual concentration-time plots by dose (on both linear and semi-log scales) against actual time post-dose (there will be separate spaghetti plots for each dose per scale), coloured by dose.
- individual concentration-time plots by participant (on both linear and semi-log scales) against actual time post-dose (there will be separate spaghetti plots for each dose per scale), coloured by dose.
- median concentration-time plots (on both linear and semi-log scales) against nominal time
  post-dose by dose (all doses on the same plot per scale, based on the summary of
  concentrations by dose and time post-dose), coloured by dose.
- mean concentration-time plots (on both linear and semi-log scales) against nominal time
  post-dose by dose (all doses on the same plot per scale, based on the summary of
  concentrations by dose and time post-dose), coloured by dose.

[figure not shown]
The scale used for the x-axis (time) of these plots will be decided on review of the data, and will depend on how long PF-07328948 concentration is quantifiable in the matrix.

For summary statistics, median and mean plots by sampling time, the nominal PK sampling time will be used. For individual participant plots by time, the actual PK sampling time will be used.

If the food effect is assessed the PK parameters will also be summarized descriptively as described above by fasting condition.

To assess any effect of food in Cohort 2 and/or Cohort 3, a mixed effects ANOVA will be performed separately on the natural log transformed AUCinf, AUClast, and Cmax (dose-normalized prior to analysis, if appropriate) with fasting condition included as a fixed effect and participant as a random effect, as described in Section 5.2.4. If performed, only data from the respective periods that includes the two treatments of interest will be included. The Kenward-Roger adjustment for the degrees of freedom will be used. Estimates of the adjusted mean differences (Test-Reference) and corresponding 90% CIs will be obtained from the model. The adjusted mean differences and 90% CIs for these differences will be exponentiated to provide estimates of the ratio of adjusted geometric means (Test/Reference) and 90% CIs for these ratios. The treatment in the fasted state will be the reference and the test treatment will be in the fed state.

### 6.4. Subset Analyses

No subset analyses will be performed.

# 6.5. Baseline and Other Summaries and Analyses

### **6.5.1. Baseline Summaries**

Demographic data (age, biological sex, race, ethnicity, weight, body mass index and height) will be summarised overall in accordance with the sponsor reporting standards.

### 6.5.2. Study Conduct and Participant Disposition

Participant evaluation groups will show participant disposition by treatment, overall and will show which participants were analyzed for PK and safety. Frequency counts and percentages will be supplied for participant discontinuation(s) by treatment. Data will be reported in accordance with the sponsor reporting standards.

### 6.5.3. Concomitant Medications and Nondrug Treatments

All prior and concomitant medication(s) as well as non-drug treatment(s) will be reported according to current sponsor reporting standards.

### 6.6. Safety Summaries and Analyses

All safety analyses will be performed on the Safety Analysis Set.

#### 6.6.1. Adverse Events

Adverse events will be listed and summarized by treatment and overall, in accordance with sponsor reporting standards using the safety analysis set defined in Section 4.

### 6.6.2. Laboratory Data

Laboratory data will be listed and summarized by treatment in accordance with the sponsor reporting standards using the safety analysis set defined in Section 4. Baseline is as defined in Section 3.5.2.

Data collected at screening that are used for inclusion/exclusion criteria, will be considered source data, and will not be required to be reported, unless otherwise noted.

#### 6.6.3. Vital Signs

Absolute values and changes from baseline in supine systolic and diastolic blood pressure, pulse rate and respiratory rate will be summarized by treatment and timepoint, according to sponsor reporting standards, using the safety analysis set defined in Section 4. Baseline is as defined in Section 3.5.3.

Mean changes from baseline for supine systolic and diastolic blood pressure, pulse rate and respiratory rate will be plotted against time post-dose. On each plot there will be one line for each treatment. Dats from all cohorts will be plotted on the same figure using a single line for the placebo group(s). Corresponding individual plots of changes from baseline will also be produced for each treatment.

Maximum increase and decrease from baseline over all measurements taken post-dose for supine systolic and diastolic blood pressures, pulse rate and respiratory rate will be summarized by treatment, according to sponsor reporting standards.

Minimum and/or maximum absolute values and changes from baseline for supine vital signs will also be summarized descriptively by treatment using categories as defined in Appendix 1.

Numbers and percentages of participants meeting the categorical criteria will be provided. All planned and unplanned post-dose time points will be counted in these categorical summaries.

Data collected at screening that are used for inclusion/exclusion criteria, will be considered source data, and will not be required to be reported, unless otherwise noted.

### 6.6.4. Electrocardiograms

Absolute values and changes from baseline in QT, heart rate, QTcF, PR and QRS will be summarized by treatment and timepoint using sponsor reporting standards, using the safety analysis set defined in Section 4. Baseline is as defined in Section 3.5.4.

Mean changes from baseline in QT, heart rate and QTcF will be plotted against time post-dose. On each plot there will be one line for each treatment. Corresponding individual plots of changes from baseline will also be produced for each treatment.

Changes from baseline in QTcF will also be plotted separately against drug concentrations of PF-07328948. This will be a scatter plot for all observations where QTcF and drug concentration are recorded. Placebo data will also be included (with drug concentration set to zero). Different symbols will be used for each treatment.

Maximum increase from baseline for QTcF, heart rate, PR and QRS values will be summarized by treatment, according to sponsor reporting standards.

ECG endpoints and changes from baseline (QTcF, PR and QRS) will also be summarized descriptively by treatment using categories as defined in Appendix 1. Numbers and percentages of participants meeting the categorical criteria will be provided. All planned and unplanned postdose time points will be counted in these categorical summaries.

Listings of participants with any single post-dose value >500msec will also be produced for QTcF.

Data collected at screening that are used for inclusion/exclusion criteria, will be considered source data, and will not be required to be reported, unless otherwise noted.

#### 6.6.5. Continuous Cardiac Monitoring

Continuous cardiac monitoring will be performed using telemetry as outlined in the protocol. Data will be reviewed and summarized on an ongoing basis during the study to evaluate the safety of participants.

All abnormal rhythms will be recorded and reviewed by the investigator for the presence of rhythms of potential clinical concern. The time, duration, and description of the clinically significant event will be recorded in the CRF. Events deemed of clinical concern will be recorded as AEs and will be summarized as part of the standard AE outputs.

#### 6.6.6. Physical Examination

Physical examinations will be performed as described in the protocol.

Medical history and physical examination as applicable, collected during the course of the study will be considered source data and will not be required to be reported, unless otherwise noted. However, any untoward findings identified on physical and/or neurological examinations conducted during the active collection period will be captured as AEs, if those findings meet the definition of an AE.

Data collected at screening that are used for inclusion/exclusion criteria, will be considered source data, and will not be required to be reported, unless otherwise noted.

#### 7. INTERIM ANALYSES

#### 7.1. Introduction

No formal interim analysis will be conducted for this study. However, as this is a sponsor-open study, the sponsor will conduct unblinded reviews of the data during the course of the study for the purpose of safety and tolerability assessment, facilitating dose-escalation decisions, facilitating PK/PD modeling, and/or supporting clinical development. Unblinded results will be reviewed by a designated limited number of sponsor colleagues within the study team.

### 7.2. Interim Analyses and Summaries

N/A

### **APPENDICES**

# Appendix 1. Categorical Classes for ECG and Vital Signs of Potential Clinical Concern

# **Categories for QTcF**

Degree of Prolongation	Mild	Moderate	Severe
Absolute value (msec)	>450 and ≤480	>480 and ≤500	>500
Increase from baseline (msec)		>30 and ≤60	>60

# Categories for PR and QRS

PR (ms)	max. ≥300	
PR (ms) increase from baseline	Baseline >200 and max. ≥25% increase	Baseline ≤200 and max. ≥50% increase
QRS (ms)	max. ≥140	
QRS (ms) increase from baseline	≥50% increase	

# **Categories for Vital Signs**

Systolic BP (mm Hg)	min. <90	
Systolic BP (mm Hg) change from baseline	max. decrease ≥30	max. increase ≥30
Diastolic BP (mm Hg)	min. <50	
Diastolic BP (mm Hg) change from baseline	max. decrease ≥20	max. increase ≥20
Supine pulse rate (bpm)	min. <40	max. >120

# **Appendix 2. Example SAS Code for Statistical Analyses**

# Mixed Effects ANOVA: (PK parameters)

```
proc mixed data = dataset method = ml;
    class subjid treattxt;
    model &var = treattxt /residual;
    random subjid;
    lsmeans treattxt / diff cl alpha = 0.1;
run;
```

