4.2. Scientific Rationale for Study Design

The population planned for this study will be healthy males and females of non-childbearing potential. Female participants will be confirmed not to be of childbearing potential because embryo-fetal development toxicity studies with PF-07328948 have not been conducted. In male participants, appropriate measures are expected to be followed to minimize potential transfer of PF-07328948 via semen to partners (see Appendix 4).

Because this is the first time PF-07328948 will be administered to humans, an escalating single, oral dose, crossover design is planned with careful assessment and ongoing review of safety, tolerability, and PK data of PF-07328948. Precautionary sentinel dosing will also be utilized in any period evaluating escalating doses of PF-07328948 to ensure that safety and tolerability data in a subset of 2 participants within each period supports testing additional participants in that period. In each period, approximately 6 participants are planned to receive PF-07328948, and approximately 2 participants are planned to receive placebo, with all the participants at the end of the study having received up to 4 doses of PF-07328948 and up to 2 placebo. The crossover design permits both within- and between-participants assessments of safety, tolerability, and PK at multiple dose levels and placebo.

In addition, the highest anticipated C_{max} and AUC_{24} of PF-07328948 will not exceed the pre-defined human exposure stopping limits nor exceed the highest feasible total daily dose Eurthermore, to permit an unbiased assessment of safety, the administration of both PF-07328948 and placebo in each period will be double-blinded to both site staff (except those involved in preparation of doses) as well as participants. To permit real-time review of the safety, tolerability, and PK data, a limited number of sponsor study team members will be unblinded.

CCI

. As a BDK inhibitor/degrader,

PF-07328948 is expected to inhibit BDK-mediated phosphorylation of BCKDH enzyme complex, resulting in an increase in BCAA/BCKA catabolism and a decrease in circulating BCAA and BCKA levels. As protein intake is known to impact plasma BCAA/BCKA levels, CCI

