9.3.2.2. Statistical Methods for PK Data

Plasma concentrations of PF-07328948 will be summarized descriptively by dose (and fasting condition, if appropriate) and nominal PK sampling time. Individual participant and median profiles of the plasma concentration-time data will be plotted by dose (and fasting condition, if appropriate) using actual (for individual) and nominal (for median) times respectively. Median profiles will be presented on both linear and log scales.

The plasma PK parameters will be summarized descriptively by dose (and fasting condition, if appropriate) as applicable. Dose-normalized AUC_{inf}, AUC_{last}, and C_{max} will be plotted against dose (and fasting condition, if appropriate) using a logarithmic scale, and will include individual participant values and the geometric means for each dose. These plots will be used to understand the relationship between the PK parameters and dose (and fasting condition, if appropriate).

If the food effect is assessed, a mixed effects ANOVA will be performed separately on the natural log transformed AUC_{inf} , AUC_{last} , and C_{max} (dose-normalized prior to analysis, if appropriate) with fasting condition included as a fixed effect and participant as a random effect. Further details of this analysis will be provided in the SAP.

Additional PK analyses may be performed if deemed appropriate, and may not be included in the CSR.

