### 5. GENERAL METHODOLOGY AND CONVENTIONS

### 5.1. Hypotheses and Decision Rules

There are no formal statistical hypotheses or decision rules in this study.

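### Food-effect ANOVA: SAP 6.3.1 requires Kenward-Roger, but the Appendix 2 code uses ML with no ddfm option; run unchanged, it makes the 90% intervals about 9–13% too narrow on the log scale

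*SAP*

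**What the plan says.** Protocol 9.3.2.2 makes the analysis conditional: "If the food effect is assessed, a mixed effects ANOVA will be performed separately" on the log-transformed AUCinf, AUClast and Cmax. SAP 6.3.1 repeats this, with fasting condition as the fixed effect and participant as the random effect. It asks for 90% intervals for the fed/fasted ratio and states: "The Kenward-Roger adjustment for the degrees of freedom will be used". For the model it refers to SAP 5.2.4, which ends with "Example SAS code is provided in Appendix 2".

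The Appendix 2 block for PK parameters begins "proc mixed data = dataset method = ml". Its MODEL statement is "model &var = treattxt /residual", followed by "random subjid" and a request for 90% limits. No ddfm option appears. The text of 5.2.4 and 6.3.1 names neither ML nor REML, so this code is the only place where the SAP gives an estimation method. SAP Table 2 marks only AUClast, AUCinf and Cmax for model-based analysis, and only for the food effect, so the block serves exactly this analysis.

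**The concern.** There are two separate discrepancies, with different consequences.

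First, the code omits the degrees-of-freedom method that 6.3.1 requires, so it does not implement the text.

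Second, the code selects maximum likelihood. ML variance estimates make no allowance for the fixed effects that were estimated. The resulting bias is negligible in large samples but material with four to six pairs. The standard error of the log ratio is too small, and so the 90% intervals are too narrow. The p-values that 5.2.4 also asks for rest on the same standard error.

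A programmer who notices only the first discrepancy would add `ddfm=kr`, believe the code now matches the text, and keep the narrow intervals. Since "There are no formal statistical hypotheses or decision rules in this study", the ratio with its interval is the main output of this comparison, and the interval should have the coverage it claims.

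**Working it through.** The documents give no interval width, degrees of freedom or within-participant SD for the food effect, so there is no stated figure to reproduce.

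**Number of pairs.** Protocol 4.2 says: "In each period, approximately 6 participants are planned to receive PF-07328948, and approximately 2 participants are planned to receive placebo". Assume that the fed and fasted periods both fall in one cohort of 8. The participants on active in both periods then number at least 6 + 6 − 8 = 4 and at most 6.

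**Complete pairs, random participant intercept.** Let SSE be the within-participant sum of squares after fitting condition.

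- ML residual variance = SSE/n; REML residual variance = SSE/(n − 1).
- SE(ML)/SE(REML) = √((n − 1)/n).
- Default (containment) df = 2n − rank[X Z] = 2n − (n + 1) = n − 1. When the between-participant variance estimate is positive, Kenward-Roger also gives n − 1 and leaves the SE unchanged. The narrowing therefore comes from `method = ml`, not from the missing ddfm option.
- Actual coverage = P(|T| < t(0.95, n − 1) × ratio), where T has n − 1 df.

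| Complete pairs | Width ratio ML/REML (log scale) | Too narrow by | Actual coverage |
|---|---|---|---|
| 6 | √(5/6) = 0.9129 | 8.7% | 87.5% |
| 5 | √(4/5) = 0.8944 | 10.6% | 87.1% |
| 4 | √(3/4) = 0.8660 | 13.4% | 86.6% |

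Numerical ML and REML/Kenward-Roger fits to simulated data gave the same median ratios: 0.913, 0.894 and 0.866.

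**Pairs plus single-condition participants.** SAP 6.3.1 does not restrict the model to complete pairs. If 6 and 6 active participants overlap by 4, the other 4 (two per condition) also enter. The random-intercept model was simulated for this layout with 6000 data sets per setting. The within-participant correlation is an assumption, as the documents give none.

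| Assumed correlation | Median width ratio, ML to REML + KR | Coverage, ML | Coverage, REML + KR | Coverage, REML at default df |
|---|---|---|---|---|
| 0.5 | 0.924 | 86.4% | 88.5% | 90.0% |
| 0.7 | 0.893 | 87.7% | 89.6% | 90.3% |
| 0.9 | 0.870 | 86.9% | 90.2% | 90.4% |

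The narrowing here is about 8–13%.

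**What this looks like on the ratio scale.** Take a true ratio of 1 and an assumed within-participant log-scale SD of 0.20. The REML interval is exp(± t(0.95, n − 1) × SD × √(2/n)); for ML the half-width is multiplied by the ratio above. For 6 pairs the half-width is 2.015 × 0.20 × √(2/6) = 0.233, or 0.212 under ML.

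| Pairs | Assumed SD | REML | ML |
|---|---|---|---|
| 6 | 0.15 | 0.84–1.19 | 0.85–1.17 |
| 6 | 0.20 | 0.79–1.26 | 0.81–1.24 |
| 6 | 0.30 | 0.71–1.42 | 0.73–1.38 |
| 4 | 0.20 | 0.72–1.39 | 0.75–1.33 |

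**The case against.** The strongest reply is that the code is labelled an example, while the sentence in 6.3.1 is a commitment. Code run unchanged would already depart from the plan. That is fair as to Kenward-Roger, and it is why the sizes above are conditional on unchanged code. It does not dispose of ML: no text excludes it, so a programmer could honour 6.3.1 in full by adding `ddfm=kr` and still obtain the narrow intervals.

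The number of pairs is also uncertain, in both directions. Under the planned allocation, an overlap of 4 brings in 4 unpaired participants, so exactly 4 complete pairs needs dropout or a different assignment. The simulated 8–13% is the better figure for that layout. If two cohorts with 6 pairs each were analysed together, the narrowing would be 1 − √(11/12) = 4.3%, with coverage of 88.7%. With only 3 complete pairs it would be 18.4%. In a minority of small data sets the participant variance is estimated at zero; Kenward-Roger df then rise, and the ML interval need not be the narrower one.

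The practical effect is modest. Coverage falls by 2.5 to 3.4 points for 6 down to 4 complete pairs, and in the illustration both intervals would be read as imprecise. The analysis is conditional and exploratory. All of this stands and limits the severity, but it does not make the code right.

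Other example code may have been blacked out. The PK block is printed whole, however, and code elsewhere would not change its options.

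**Conclusion.** The concern holds. SAP 6.3.1 and the Appendix 2 code contradict each other on the degrees of freedom, and the code specifies an estimation method unsuited to so few pairs. If it is run as printed, the log-scale 90% intervals are 8.7% too narrow with 6 complete pairs, rising to 13.4% with 4, and cover 87.5% down to 86.6%. With 4 pairs plus 4 single-condition participants the narrowing is about 8–13% over assumed correlations of 0.5 to 0.9.

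The complete-pair percentages are exact given the number of pairs and a positive between-participant variance estimate. The range of 4 to 6 pairs rests on both periods lying in one cohort of 8. The schema is not shown and assignments may change.

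Consequences are limited to the food-effect intervals and p-values. With complete pairs the point estimates are the same under either method. The primary safety summaries and the descriptive secondary PK summaries are untouched. This should be corrected, but it does not threaten the study's main objectives.

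**What to change.** In the Appendix 2 block for PK parameters, replace `method = ml` with `method = reml` and add `ddfm=kr` to the MODEL statement. Name REML as the estimation method in SAP 5.2.4 or 6.3.1. Both code changes are needed: REML removes the narrowing, and `ddfm=kr` makes the code follow 6.3.1.

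The cost is two options and a few words. The intervals widen on the log scale by a factor of 1/0.9129 = 1.095 with 6 complete pairs and 1/0.8660 = 1.155 with 4, which restores 90% coverage. With unpaired records and a low correlation, Kenward-Roger can fall slightly short (88.5% in the simulation at correlation 0.5), but that still exceeds the 86.4% under ML.

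If ML is in fact intended, 6.3.1 should say so and give the reason. That would settle the contradiction but leave the intervals too narrow.
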